This study employs an **experimental research design** utilizing **randomized assignment** and **repeated measures**. Participants who consent to the study will be allocated to either the experimental group (Group A) or the control group (Group B). Group A participants will listen to self-selected music in addition to receiving standard care. Group B participants will receive standard care only. The objective is to evaluate the effectiveness of music therapy in alleviating fatigue. A total of 44 patients with leukemia undergoing their initial chemotherapy will be recruited, with 22 participants allocated to each group.

The measurement process will be conducted in two parts:

1. **Primary Data Collection:** Data will be collected at two main time points: upon admission for initial chemotherapy (Baseline, T0) and on Day 21 of the

chemotherapy cycle (T1). On Day 21, the researcher will visit the ward to collect the required data, including the Tang's Fatigue Scale, the Fatigue Numerical Rating Scale (NRS), and clinical laboratory data. If a participant has been discharged, data will be collected via telephone interview or an online questionnaire.

2. **Symptom Diary:** Participants will record their fatigue levels using the Fatigue NRS immediately following each music therapy session.

Baseline demographic data will be collected only at T0. The measurement time points and the application of corresponding instruments are detailed in Table 3-2.

Table 1: Schedule of Research Measurements

Time	Before Chemo (T0)	Chemo Day 7	Chemo Day 14	Chemo Day 21 (T1)
Tang's Fatigue Scale	○			○
Numerical Rating Scale (NRS)	○	○	○	○
WBC	○			○
Hemoglobin	○			○
Albumin	○			○
Demographic Data	○			

Note: ○ = Data to be collected

Research Setting and Participants

This study will be conducted in the hematology-oncology ward of a medical center located in Northern Taiwan. Participants must meet the following inclusion criteria:

1. Clinically diagnosed with Acute Myeloid Leukemia (AML) by a specialist physician.
2. Scheduled to receive initial (first-time) chemotherapy.
3. Aged 20 years or older.
4. Able to communicate in Mandarin or Taiwanese.
5. Possess normal hearing ability.
6. No history of psychiatric illness and clear consciousness.
7. No prior participation in any fatigue management intervention study.
8. Understands the research purpose, voluntarily agrees to participate, and has signed the informed consent form.

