Prior to study commencement, approval will be obtained from the Institutional Review Board (IRB). Following IRB approval, and after explaining the study to and receiving consent from the attending physicians and ward nursing staff, the researcher will conduct participant recruitment in the inpatient wards and outpatient clinics. Individuals who meet the inclusion criteria will be identified as potential participants. The researcher will explain the study's purpose and methodology to these individuals. After obtaining informed consent and a signed consent form, the researcher will administer the pre-test (T0) questionnaires. This packet includes the Demographic Data Sheet, the Tang Fatigue Rating Scale (TFRS), the G-8 screening tool, and the symptom diary. This self-administration process is expected to take approximately 10 minutes. If a participant is unable or unwilling to self-report (e.g., due to advanced age or fatigue), the researcher will conduct a structured interview to complete the questionnaires, which is estimated to take 30–40 minutes. Concurrently, all participants will be invited to join the study's official LINE group for communication. Following the collection of baseline questionnaires, a computer-generated randomization sequence will be implemented by personnel not directly involved in the study (i.e., someone other than the principal investigator) to allocate participants to either the experimental group (Group A) or the control group (Group B). Participants in Group A, after confirming their chemotherapy infusion line is properly connected, will begin listening to 30 minutes of self-selected music while concurrently receiving standard care. Participants in Group B will receive standard care only. A total of **60 participants** with Acute Myeloid Leukemia (AML) undergoing chemotherapy are expected to be recruited (n=30 per group). Both groups will be required to complete the symptom diary throughout the 21-day

study period (est. 1 minute per entry). Group A will complete the Fatigue Numerical Rating Scale (NRS) immediately following each music therapy session. Group B will complete the Fatigue NRS 30 minutes after the commencement of their chemotherapy infusion.

On Day 21 (T1), the researcher will collect the post-test data (TFRS, NRS, and G-8) in the ward. If a participant has been discharged, data will be collected via telephone interview or an online questionnaire.

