The laboratory data required for this study (WBC, Hb, Albumin) will be obtained by the researcher through a medical record review. Data from blood samples drawn as part of standard clinical care, taken before chemotherapy (T0) and on Day 21 (± 3 days) (T1), will be utilized. **No additional blood draws will be required for this study.**

Throughout the study period, participants may ask questions at any time via the official LINE group, and the researcher will provide responses.

Ethical Considerations

This study will be initiated only after obtaining approval from the Institutional Review Board (IRB) and securing consent from the nursing administrators and attending physicians of the recruitment site. Prior to formal enrollment, the researcher will personally explain the study's purpose, procedures, and methodology to each potential participant.

The researcher will address all participant inquiries. Participants will be explicitly informed that their participation is voluntary, that they may withdraw from the study at any time without penalty, and that their decision will not affect the quality of their medical treatment or nursing care in any way.

All research data collected from participants will be processed using anonymous coding. The data will be securely stored by the researcher and used exclusively for academic purposes. Confidentiality will be strictly maintained, and data will not be publicly disclosed or used for other purposes, ensuring the protection of participant privacy.

Data Processing and Statistical Analysis

1. Data Management The researcher will review all questionnaires for completeness. All collected data will be coded and entered into the Statistical Packages for the Social Sciences (SPSS) version 26.0 for data processing and management.

2. Statistical Analysis In accordance with the study's objectives, data analysis will be divided into descriptive and inferential statistics, as outlined in Table 3-3.

- **a. Descriptive Statistics:** Based on the characteristics of the variables, data

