will be categorized into four measurement scales: nominal, ordinal, interval, and ratio (Kaur et al., 2018). Nominal and ordinal scale data are considered **categorical variables** (e.g., sex, education level, occupation, perceived economic status, marital status, religious beliefs, and chemotherapy drug names) and will be presented as frequencies (n) and percentages (%). Interval and ratio scale data are considered **continuous variables** (e.g., age, fatigue severity, Absolute Neutrophil Count [ANC], hemoglobin, and albumin) and will be presented using means, standard deviations (SD), and ranges (minimum and maximum) (Kaur et al., 2018).

- **b. Inferential Statistics:** This study utilizes an experimental design with longitudinal follow-up and repeated measures, analyzed on an **intention-to-treat (ITT)** basis. It will compare the differences in fatigue severity and clinical laboratory values between the music therapy and control groups. During the study, data attrition may occur due to factors such as disease progression or a participant's personal decision to withdraw, leading to unequal sample sizes at different measurement points. Therefore, this study will employ **Generalized Estimating Equations (GEE)** to analyze the relationship between the independent and dependent variables. GEE will be used to compare pre- and post-test values (fatigue severity, Absolute Neutrophil Count [ANC], hemoglobin, and albumin) between the experimental and control groups. A *p*-value of < 0.05 will be considered the standard for statistical significance (Ziegler & Vens, 2010).

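### The diary NRS is triggered by a music session in Group A and by an infusion in Group B, so the interim and daily fatigue ratings can go selectively missing by arm; the Day 21 comparison is not exposed

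*Combined protocol and SAP*

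**What the plan says.** All places are in the combined protocol and SAP.

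- **Group A's rating.** Research Procedures: "Group A will complete the Fatigue Numerical Rating Scale (NRS) immediately following each music therapy session". The Symptom Diary item of Research Design uses the same trigger without naming an arm: "Participants will record their fatigue levels using the Fatigue NRS immediately following each music therapy session".
- **Group B's rating.** Research Procedures: "Group B will complete the Fatigue NRS 30 minutes after the commencement of their chemotherapy infusion".
- **General diary duty.** Research Procedures: "Both groups will be required to complete the symptom diary throughout the 21-day" study period.
- **Schedule.** Table 1 in Research Design lists the NRS at T0, Day 7, Day 14 and Day 21. The TFRS and the laboratory values appear at T0 and Day 21 only.
- **Day 21.** Research Procedures: "On Day 21 (T1), the researcher will collect the post-test data (TFRS, NRS, and G-8) in the ward". For those who have gone home: "If a participant has been discharged, data will be collected via telephone interview or an online questionnaire".
- **Adherence.** The Music Therapy Protocol plans a session every day for 21 days and uses the same diary to confirm adherence in the experimental group.
- **Leaving.** Ethical Considerations tells participants that "they may withdraw from the study at any time without penalty". The Inferential Statistics item says that "data attrition may occur due to factors such as disease progression or a participant's personal decision to withdraw".
- **Analysis.** The same item claims an intention-to-treat basis and uses GEE to compare values before and after the intervention between the arms. It refers to fatigue severity without naming the instrument. Research Instruments names the TFRS as the primary outcome measure.

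The documents do not say what a Group A participant records on a day without music or after giving music up. Nor do they say what a Group B participant records on a day without an infusion.

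**The concern.** An intention-to-treat comparison needs outcomes to be sought in the same way whether or not the participant keeps to the intervention. Here the event that makes a diary rating due in Group A is the intervention itself. If someone is too tired for the session and follows the stated trigger, no rating falls due that day. A fatigued Group B participant with an infusion still has one due.

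If skipping goes with fatigue, Group A's diary loses its worse days and the arm looks better than it is. Standard GEE on the ratings that were recorded does not repair this, because whether a rating is missing then depends on the value that was not recorded. Because the diary also serves as the adherence record, a blank may mean no session, or a session after which the rating was forgotten. The diary form is not in the documents, so it cannot be seen whether it separates the two.

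At stake are the daily NRS series and the Day 7 and Day 14 NRS, for which no other collection procedure is described. A rating that was never requested cannot be recovered at analysis.

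**Working it through.** **1. Which outcomes depend on the trigger**

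| Outcome | Scheduled points | Described source | Depends on a session or infusion? |
|---|---|---|---|
| TFRS | T0, Day 21 | Before randomisation; researcher at Day 21 | No |
| NRS | T0, Day 21 | Before randomisation; researcher at Day 21 | No |
| NRS | Day 7, Day 14 | Diary only | Yes |
| NRS | Other diary days | Diary only | Yes |
| Laboratory values | T0, Day 21 | Medical record | No |

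Two of the four scheduled NRS points are exposed, together with the other daily entries. Neither TFRS point is.

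**2. Do Day 7 and Day 14 enter the analysis?**

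The analysis text speaks of values before and after. The sample size may point the other way. Inputs from Sample Size Calculation: effect size 0.21, α = 0.05, power 0.80, N = 34. The number of measurements m, the correlation ρ and the metric of the effect size are not stated. Treating 0.21 as f in a repeated-measures within-between F test with two groups:

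λ = f²·N·m/(1 − ρ), df = (m − 1) and (N − 2)(m − 1).

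- m = 4, ρ = 0.5: λ = 0.0441 × 34 × 4/0.5 = 12.0; required N = 34, power 0.823. This reproduces the plan's figure.
- m = 2, ρ = 0.5: λ = 0.0441 × 34 × 2/0.5 = 6.0; required N = 48, power at N = 34 is 0.66.
- m = 2, ρ = 0.7: required N = 30.

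Four measurements with ρ = 0.5 fit. But with m = 2 the requirement falls from 48 to 30 as ρ goes from 0.5 to 0.7, so some ρ in between would also give 34. The figure suggests four NRS points and does not prove it.

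**3. Size of the bias in a diary-day mean**

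All inputs are assumptions: no true effect, a fraction s of Group A sessions skipped, correlation ρ between the tendency to skip and that day's fatigue (both normal), and no selective loss in Group B. With z the (1 − s) quantile of the standard normal:

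bias in the observed Group A mean = −ρ·φ(z)/(1 − s), in SD units.

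- s = 0.1, ρ = 0.3: −0.3 × 0.1755/0.9 = −0.058 SD
- s = 0.2, ρ = 0.5: −0.5 × 0.2800/0.8 = −0.175 SD
- s = 0.3, ρ = 0.7: −0.7 × 0.3477/0.7 = −0.348 SD
- ρ = 0: bias 0 for any s

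With an assumed NRS SD of 2.5, the middle case is 0.175 × 2.5 = 0.44 points.

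**4. Cross-check with a different missingness model**

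Simulation with no true effect, NRS SD 2, within-person correlation 0.5 and Group B complete. The odds of skipping are multiplied by OR per SD of current fatigue. Day 7 difference, A minus B, in NRS points:

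| Skipped | OR 1 | OR 1.5 | OR 2 | OR 3 |
|---|---|---|---|---|
| 10% | −0.01 | −0.07 | −0.13 | −0.20 |
| 20% | 0.01 | −0.15 | −0.26 | −0.37 |
| 30% | −0.01 | −0.23 | −0.38 | −0.54 |
| 40% | −0.01 | −0.30 | −0.51 | −0.72 |

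At 10–30% skipped and OR 1.5–3 this is 0.07/2 = 0.035 SD to 0.54/2 = 0.27 SD, the same direction and order as step 3. The Day 21 difference stays within 0.02 of zero, by construction, because that assessment does not depend on music.

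**The case against.** The strongest reply is that the plan already asks for these ratings. Both groups must keep the diary throughout, and Table 1 lists Day 7 and Day 14 without regard to arm. The session sentence may only time the entry on days with a session. On a day with both a session and an infusion the triggers coincide, since the 30 minutes of music start with the infusion. This reading is possible, but it leaves a Group A participant without a rating time on a day without music. The general duty and the specific trigger have to be reconciled in the text.

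A second reply is that Group A is not the only arm with gaps. This stands. Group B's rating needs an infusion, and no rule covers days without one or days after discharge. Group B could even have more gaps, since sessions are planned daily. The documents do not give the number of infusion days, so the net direction is not fixed. The figures above assume no selective loss in Group B.

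A third reply is that the direction is assumed. This also stands: nothing in the documents shows that tired patients skip listening rather than listen more.

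Two stronger readings are tempting. A reader might infer that a participant who stops music yields no further NRS data and that the intention-to-treat comparison therefore fails. The documents do not support that: the stated contrast is before versus after, and the researcher collects the Day 21 TFRS and NRS whatever happened with music. A reader might also infer that stopping music counts as withdrawal and so costs the Day 21 TFRS. Nothing in the documents says so; the text on leaving concerns withdrawal from the study.

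**Conclusion.** The point holds for the diary NRS, including Day 7 and Day 14, and no further. The rating triggers differ by arm, each can fail to occur, and Group A's depends on adherence under an analysis described as intention-to-treat.

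If skipping rises with fatigue, the observed Group A diary mean is about 0.06–0.35 SD too low for 10–30% of sessions skipped and correlations of 0.3–0.7. If skipping is unrelated to fatigue, the bias is zero. Skip rate, correlation, SD and complete Group B diaries are all assumptions, and the figures describe a diary-day mean. They must not be read as bias in the TFRS result or in the before-and-after contrast, which is not defeated. The consequence for inference is larger if the Day 7 and Day 14 NRS enter the GEE, and the plan leaves that open. The change is worth making because it is nearly free and the lost ratings cannot be reconstructed.

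**What to change.** 1. In the Symptom Diary item of Research Design and in Research Procedures, make the NRS due in both arms at the same set time on each diary day, whether or not a music session or an infusion took place. State that Day 7 and Day 14 are due for every randomised participant.
2. Record the session (yes/no, minutes) in a field separate from the rating, if the diary does not already do so.
3. In Ethical Considerations and the Inferential Statistics item, separate stopping music from withdrawing consent for data collection. State that a participant who stops music stays in follow-up, keeps the diary and the Day 21 assessments, and is analysed in Group A unless consent for data collection is withdrawn. Laboratory values continue to come from the record on the same terms.
4. In the Inferential Statistics item, state whether the Day 7 and Day 14 NRS enter the GEE and how missing diary entries are handled.

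Cost: revised diary wording, possibly one extra field, a short amendment, and a few more one-minute entries for participants on days without music or infusion. No extra visits or blood draws are needed.

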9. Willing to cooperate with all study procedures during the research period.

Participants will be **excluded** from the study if they meet the following criteria:

1. Severe hearing impairment.

2. Unstable vital signs or unclear consciousness.

III: Sample Size Calculation

The sample size was estimated based on the **Generalized Estimating Equations (GEE)** approach for repeated measures. The analysis will control for baseline demographic and disease characteristics as covariates (e.g., age, sex, education level, occupation, perceived economic status, marital status, religious beliefs, and metastasis). The dependent variables are fatigue, White Blood Cell (WBC) count, hemoglobin, and albumin.

The calculation was performed using G*Power software (version 3.1.9.7). Parameters were set as follows: a significance level (α) of 0.05, statistical power ($1-\beta$) of 0.80, a 95% confidence interval, and an anticipated **effect size of 0.21**. This calculation yielded a required sample size of 34 participants (as shown in Figure 3-2). To account for a potential attrition rate of 30%, the study aims to recruit a total of **44 participants** ($n=22$ for Group A, $n=22$ for Group B).

Music Therapy Protocol

1. Music Selection, Dosage, and Headphone Use

According to the literature, a music therapy duration of 15–30 minutes is effective for fatigue alleviation (Burns et al., 2008; Cassileth et al., 2003; Miladinia et al., 2021; Reimnitz et al., 2020; Sezgin & Bektas, 2022). Music selection will be based on individual preferences and cultural background (Tsai & Chou, 2015; Browning, 2000; Gerdner, 2000).

To ensure data integrity while considering the patient's length of stay, physical burden during chemotherapy, and protocol adherence, the music therapy intervention in this study will be administered **once daily for 21 consecutive days**. The **30-minute intervention** will commence at the start of the chemotherapy infusion. During the study, participants will be provided with a chemotherapy symptom tracking diary to confirm adherence to the music therapy protocol in the experimental group.

For reasons of personal hygiene, preference, and potential patient discharge, participants will be asked to use their own headphones. If a participant does not have headphones, a set will be provided by the researcher.

Research Instruments and Psychometric Properties

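### GEE is the only inferential method for about 31 to 44 patients and no small-sample correction is named; if run uncorrected, the two-visit 5% test has a true size of about 6 to 7% and its 95% intervals are 5 to 8% too narrow

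*Combined protocol and SAP*

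**What the plan says.** Under Data Processing and Statistical Analysis, b. Inferential Statistics, the plan gives attrition and unequal numbers across time points as its reason for choosing GEE: "Therefore, this study will employ Generalized Estimating Equations (GEE) to analyze the relationship between the independent and dependent variables". The comparison described is pre-test against post-test between the two arms. On the decision rule, it says that a *p*-"value of < 0.05 will be considered the standard for statistical significance". SPSS 26.0 is named for data processing and management. The text available does not give the working correlation, the standard error (robust or model-based), the reference distribution or any small-sample adjustment. Table 3-3, which is said to outline the analysis, is not in that text.

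Under Sample Size Calculation, the inputs are "a significance level (α) of 0.05", power 0.80, and "a 95% confidence interval, and an anticipated effect size of 0.21". "This calculation yielded a required sample size of 34 participants", raised to 44 (22 per arm) for 30% attrition. Research Procedures instead expects 60 (30 per arm).

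In the schedule of measurements, the Tang fatigue scale (TFRS, the named primary outcome measure) and the laboratory values have two time points, T0 and Day 21. Only the fatigue NRS has four.

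**The concern.** The robust variance of GEE, and the Wald chi-square test usually attached to it, are large-sample tools. With 15 to 22 patients per arm the uncorrected sandwich variance is biased downward. The chi-square (or z) reference also ignores the uncertainty in that variance. Both errors make p-values too small and intervals too short.

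This arises with no covariates, no missing data and a single outcome. Settling the covariate list, the handling of dropout or multiplicity would therefore not remove it. At stake is the calibration of the trial's tests and confidence intervals, including the primary fatigue comparison.

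**Working it through.** **Inputs.** From the documents: two-sided 5% level (sidedness is not stated; a Wald chi-square test is two-sided), 1:1 allocation, total N of 34, 44 or 60, 30% attrition, two visits for TFRS and laboratory values, four for the NRS. Assumed: Gaussian outcomes, complete data, free group-by-visit means, uncorrected robust standard error, chi-square reference.

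**The plan's own figures.** An effect size of 0.21 read as Cohen's f, in a repeated-measures F test of the group-by-time interaction with four visits and correlation 0.5 (both assumed), has noncentrality 0.21² × 34 × 4 / (1 − 0.5) = 12.0. Power is 0.823 at N = 34. Two visits with the same correlation would need 48. So 34 can be reproduced, but only with inputs the plan does not state. The 44 is 34 × 1.3 = 44.2. After 30% loss, 44 × 0.7 = 30.8, about 31 patients; 60 × 0.7 = 42.

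**Two-visit test (1 df).** With n per arm, the uncorrected sandwich variance of the group difference in change is (n − 1)/n times the unbiased one. The test therefore rejects when the ordinary t statistic exceeds 1.96 × √((n − 1)/n), and its true size is

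P(|t on 2n − 2 df| > 1.96 × √((n − 1)/n)).

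At n = 22 the cut-off is 1.96 × √(21/22) = 1.915, where the t test on 42 df needs 2.018. The size is 6.2% and the interval width ratio is 1.915/2.018 = 0.949.

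**Model-based alternative.** With a pooled variance and a z reference, size is P(|t on 2n − 2 df| > 1.96).

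**Joint test (3 df, four visits).** Under the same conditions the Wald statistic is a rescaled Hotelling T². Its size is the T² tail beyond 7.815 × (n − 1)/n.

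| Total N | Robust, 1 df | CI width against t-based | Model-based z, 1 df | Robust, joint 3 df |
|---|---|---|---|---|
| 30 | 6.9% | 0.924 | 6.0% | 10.5% |
| 31 | 6.8% | 0.927 | 6.0% | 10.3% |
| 34 | 6.6% | 0.933 | 5.9% | 9.8% |
| 42 | 6.3% | 0.946 | 5.7% | 8.7% |
| 44 | 6.2% | 0.949 | 5.7% | 8.5% |
| 60 | 5.9% | 0.963 | 5.5% | 7.5% |

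**Simulation check** (2,500 to 4,000 trials per case, exchangeable working correlation).
- Two visits, complete data, robust: 6.3% at N = 44 and 7.7% at N = 30. The simulation standard error is about 0.4 to 0.5 points, so these are compatible with the exact values.
- N = 44 with 30% dropout, robust: 7.2% for two visits; for four visits, 6.7% for the Day 21 contrast alone and 9.5% for the joint test. Adding 10 covariates gave 7.3%, 8.1% and 9.8%.
- Two visits, complete data, model-based: 6.5% at N = 44 and 8.0% at N = 30. The closed-form 5.7 to 6.0% is therefore not an upper bound, and switching to that standard error is not a remedy.
- Mancl-DeRouen sandwich with a t or F reference on N − 2 df: 4.0 to 5.3% for the single contrast and 4.7 to 6.0% for the joint test, over 30 to 60 patients, with and without dropout and covariates.

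**The case against.** The strongest reply is that the plan never says it will use a robust standard error or a chi-square reference, and that the analysis table it cites cannot be seen. That stands: the finding is conditional on uncorrected GEE. It does not dispose of the point, because neither of the two usual uncorrected choices holds the 5% level at this size, and the visible text names nothing else.

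A reader might also infer the following, which the documents do not support:
- **That size reaches 8 to 11% because there are four visits.** That range belongs to a joint 3-df group-by-visit test. The plan describes a pre/post comparison, and only the NRS has four visits. A single Day 21 contrast from a four-visit model stays at about 6 to 7% (8.1% in the one simulated case with 10 covariates).
- **That planning used an F test and analysis a chi-square test.** The plan says its sample size was based on GEE and run in G*Power, and the figure showing the run is missing. The F-test origin of 34 is an inference from assumed inputs.
- **That the range of 30 to 44 patients is settled.** Research Procedures says 60. With all 60 complete, the two-visit size is 5.9%.

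It is also fair to say that the inflation is small for the primary outcome: 6.2% at 44 complete patients. That limits the weight of the point without removing it.

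**Conclusion.** The concern holds in conditional form. If uncorrected robust GEE with a Wald chi-square test is used, the pre/post test for TFRS and the laboratory values runs at about 6.2 to 6.9% for 44 down to 30 patients. Coverage of nominal 95% intervals is about 93 to 94%. A result whose exact t-based p-value is as high as 0.062 (N = 44) or 0.069 (N = 30) would be declared significant. At 60 complete patients the intervals are still about 4% too narrow. Only a joint 3-df test on the NRS would take size to about 8.5 to 10.5% (7.5% at 60).

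These closed-form figures assume Gaussian, complete data and equal arms; in simulation, 30% dropout moved the two-visit figure at 44 recruited to 7.2%. This is more than a missing detail, since standard GEE followed as written gives mildly wrong error bars. It should be changed, but at this size it does not by itself undermine the trial.

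**What to change.** In b. Inferential Statistics:

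1. Name the tested contrast: the group difference in change from T0 to Day 21.
2. Replace plain GEE Wald inference with one of two options. Either use GEE with a stated working correlation, a bias-corrected sandwich (Mancl-DeRouen or Kauermann-Carroll) and a t or F reference on between-patient degrees of freedom; or use a linear mixed model with Kenward-Roger or Satterthwaite degrees of freedom.
3. Take all confidence intervals from that same model.
4. If the mixed model is chosen, state how baseline is handled. With two visits, complete data and free group-by-visit means, it is a change-score t test. It behaves like ANCOVA only if the baseline means are constrained equal across arms.

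The recruitment target (44 or 60) should also be reconciled, since the size of the problem depends on it.

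The cost is a few sentences, with no change to design, data collection or patient burden. P-values become slightly larger. For the single contrast, an effect giving 80% power with the t reference would have shown nominal power of 84.0% at N = 30 or 82.7% at N = 44 under the uncorrected test, so about 3 to 4 points are given up. For a joint 3-df test the loss is greater: with f = 0.21, four visits and correlation 0.5, power falls from 87% to 78% at N = 34 and from 83% to 72% at N = 30. The power given up is the part bought by the inflated error rate.
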